## **Statement of Compliance:**

The trial will be conducted in accordance with International Conference on Harmonisation (ICH) Good

Clinical Practice (GCP), and applicable United States (US) Code of Federal Regulations (CFR). The Principal Investigator will assure that no deviation from, or changes to, the protocol will take place without prior agreement from the Sponsor and documented approval from the Institutional Review Board (IRB), except where necessary to eliminate an immediate hazard(s) to the trial participants. All personnel involved in the conduct of this study have GCP training. The study is conducted also under the Declaration of Helsinki. The protocol, informed consent form(s) [ICF(s)], recruitment materials, and all participant materials will be submitted to the IRB for review and approval. Approval of both the protocol and the consent form must be obtained before any participant is enrolled. Any amendment to the protocol will require review and approval by the IRB before the changes are implemented to the study. All changes to the consent form will be IRB approved; a determination will be made regarding whether a new consent needs to be obtained from participants who provided consent using a previously approved consent form.

## **Protocol Summary:**

### **SYNOPSIS**

**Title:** Effect of Cequa TM in Subjects With Dry Eye Disease That Is Currently Inadequately Controlled While on Cyclosporine 0.05% Ophthalmic Emulsion

### **Study Description:**

#### **Objectives:**

This is a phase 4, multicenter, open-label, single-arm, 12-week study of subjects with dry eye disease (DED) that is inadequately controlled by cyclosporine (CsA) 0.05% ophthalmic emulsion. Treatment will be one drop of CsA 0.09% ophthalmic solution (Cequa) in each eye twice daily (BID) for 12 weeks. The study hypothesis is that CsA 0.09% ophthalmic solution will show improved clinical benefit in subjects whose dry eye signs and/or symptoms are inadequately controlled while on CsA 0.05% ophthalmic emulsion.

**Primary:** to evaluate improvement in the signs and/or symptoms of DED following use of CsA 0.09% ophthalmic solution in subjects whose DED is inadequately controlled by CsA 0.05% ophthalmic emulsion.

**Secondary:** to evaluate changes in additional signs and symptoms over the 12-week course of Cequa therapy.

### **Statistical Analyses:**

Neither masking nor randomization will be employed for operation of this study; this is an open-label study

- Primary efficacy endpoints will be analyzed using descriptive statistics and restricted maximum likelihood repeated measures mixed model (REMLMMRM) models.
- Multiplicity adjustments of observed significance levels for primary efficacy endpoints will be presented.

### **Study Population:**

Subjects will have DED that is not adequately controlled (ie, still symptomatic and/or still exhibiting signs of disease) by current treatment with CsA 0.05% ophthalmic emulsion. Eligible subjects must have been taking CsA 0.05% ophthalmic emulsion treatment for at least 3 months prior to the Screening/Baseline visit. However, subjects who have failed prior treatment with CsA 0.05% ophthalmic emulsion will be excluded from the study.

### **Inclusion/Exclusion Criteria:**

Inclusion Criteria:

1. Male or female subjects with a history of bilateral dry eye disease for a period of at least 3 months.
2. Aged of at least 18 years.
3. Subjects with total corneal fluorescein staining  $\geq 6$  or corneal fluorescein staining in an individual zone  $\geq 2$  as per National Eye Institute Grading Scale.
4. Subjects with modified symptom assessment in dry eye global symptom score,  $\geq 40$  using visual analogue scale.
5. Subjects with best-corrected visual acuity 20/200 or better in both eyes at the Screening/Baseline visit

Exclusion Criteria:

1. Subjects who have used cyclosporine 0.05% ophthalmic emulsion in both eyes for less than 3 months prior to the Screening/Baseline visit.
2. Subjects with history of treatment failure with cyclosporine 0.05% ophthalmic emulsion.
3. Subjects who have active seasonal and/or perennial allergic conjunctivitis in either eye.
4. Subjects who had already Use initiated any systemic or topical ocular medication.

**Justification of Dose:**

Cyclosporine 0.09% ophthalmic solution (Cequa) is approved by the FDA to increase tear production in patients with KCS (Cequa prescribing information, 2018). It is to be dosed as 1 drop BID (approximately 12 hours apart) into each eye. Therefore, the dosing in the current phase 4 study will match the approved dosing regimen.

**Overall Design:**

This is a phase 4, multicenter, open-label, single-arm, 12-week study of subjects with DED that is inadequately controlled by CsA 0.05% ophthalmic emulsion. Study subjects will be male or female, at least 18 years of age, with a history and clinical diagnosis of bilateral DED for a period of at least 3 months, corrected BCVA of 20/200 or better in both eyes at the Screening/Baseline visit, and a willingness to discontinue use of all dry eye therapy, aside from continuing any existing ATP use. In addition, subjects must have total CFS ~6 (or CFS ~2 in an individual zone) and/or a modified SAnDE score ~40.

At the Screening/Baseline visit, sites will obtain signed informed consent, medical/ocular/concomitant medication histories, and demographics, perform a urine pregnancy test (for women of childbearing potential only), conduct screening ophthalmic examinations, and review inclusion/exclusion criteria. Site staff will dispense study medication, provide appropriate instructions for use, and supervise administration of first dose. All enrolled subjects will self-administer 1 drop of CsA 0.09% ophthalmic solution in each eye BID for 12 weeks. Subjects will return at Weeks 4, 8, and 12. In addition, at the Week 12 visit, sites will perform a urine pregnancy test (for women of childbearing potential only), and subjects will answer a treatment preference question. At each visit, concomitant medications will be updated, adverse events (AEs) will be collected, the subject's daily diary on the frequency of ATP and CsA 0.09% ophthalmic solution use will be examined, subjects will answer a compliance question, and actual daily use entered into electronic data capture (EDC).

**Study Record Retention:**

Investigators should retain study-related records at the site for a minimum of 5 years after study closeout.

Official Title: Effect of Cequa™ in Subjects with Dry Eye Disease That Is Currently Inadequately Controlled While on Cyclosporine 0.05% Ophthalmic Emulsion

Document: Statistical Analysis Plan (SAP)

NCT number: NCT04357795

Date: 25-Jan-2023

Statistical Analysis Plan

Effect of Cequa® in Subjects with Dry Eye Disease That Is Currently Inadequately Controlled While on Cyclosporine 0.05% Ophthalmic Emulsion

Study Phase Phase IV Product Name: Cequa®

Study/Protocol Number: OTX101-2019-001 Formulation: Cyclosporine 0.09% ophthalmic emulsion Sponsor: Sun Pharmaceuticals Industries, Ltd.

Date: 25 JAN 2023

This document presents the statistical analysis plan (SAP) for Sun Pharma Industries Ltd., Protocol No. OTX101-2019-001, Effect of Cequa® in Subjects with Dry Eye Disease That Is Currently Inadequately Controlled While on Cyclosporine 0.05% Ophthalmic Emulsion. Dry eye disease is a common, multifactorial, ophthalmologic disorder of the tears and ocular surface characterized by symptoms of burning, stinging, itching, grittiness, scratchiness, foreign body sensation, dryness, stickiness, and tired eye sensation. The onset of symptoms is usually gradual, bilateral, and chronic. Symptoms typically become more bothersome later in the day and are intensified by various environmental factors.

The goal of this study is to evaluate the clinical benefits of switching to CsA 0.09% ophthalmic solution in subjects whose DED is inadequately controlled while on CsA 0.05% ophthalmic emulsion. This analysis plan is based on the final protocol (Version 1.0) dated 11 FEB 2020. The SAP provides the description of the analyses for the Final Analysis.

Study Objectives:

This study will be carried out with the intention to answer specific questions relating to clinical performance, efficacy and safety (i.e. residual risks) of the study medication when used in accordance with its approved labelling.

1: Primary Objective

The primary objective of this study is to evaluate improvements in the signs and/or symptoms of DED following the use of CEQ in subjects whose DED is inadequately controlled by cyclosporine 0.05% ophthalmic emulsion.

2: Secondary Objective

The secondary objective of this study is to evaluate changes in additional signs and/or symptoms over the 12-week course of CEQ therapy.

The primary endpoint is as follows:

-the mean CFB in total CFS and the mean CFB in modified SAnDE score at Week 12 for all patients

The secondary endpoints are as follows:

- Mean CFB in total conjunctival staining score at Week 12
- Mean CFB in central corneal staining score at Week 12
- Mean CFB in tear osmolarity at Week 12
- Mean CFB in frequency of ATP use at Week 12
- Mean CFB in unanaesthetized Schirmer's score at Week 12
- Percentage (%) of subjects who prefer study treatment over prior treatment at Week 12

Overall Study Design

This is an open-label, multisite, single-arm, phase IV clinical study that will evaluate the efficacy of Cequa™ cyclosporine 0.09% ophthalmic emulsion in patients with DED that is not well controlled by cyclosporine 0.05% ophthalmic emulsion. Subjects will be enrolled in up to 10 clinical sites throughout the United States. Informed consent will be obtained prior to any study specific procedure is performed.

Subjects who withdraw or are withdrawn/discontinued from the study after they have signed the informed consent and received the study treatment will not be replaced. This is an Electronic Data Capture (EDC) study utilizing web-based electronic case report forms. The study is designed using Celes web-based EDC system. KCT Data Management, Inc. will manage the EDC system according to their standard operating procedures throughout the study.

Analysis Populations:

Two analysis populations will be defined for this study: Safety (SAF) and Intent-to-Treat (ITT). The determination of which subjects will be included in each population will be made prior to locking the final database. All efficacy variables will be analyzed using the ITT set of subjects, and all safety variables will be analyzed using the SAF set of subjects.

Safety Analysis Population:

All patients who receive at least 1 dose of the study medication will be included in the SAF population. No subjects (or data) will be excluded because of protocol deviations that occur during the study.

Intent-to-Treat Population:

The Intent-to-Treat (ITT) population will be comprised of all subjects who receive at least 1 dose of the study medication and have at least 1 post-baseline assessment. Following the ITT principle, subjects will be analyzed irrespective of dosing compliance or any deviations in the study medication received.

Efficacy Analyses:

The efficacy analysis will be performed after all subjects have completed Week 12 or discontinued prior to Week 12, and after the study database has been cleaned, verified, and locked. All efficacy analyses will be performed using the ITT population. All analyses will be implemented using SAS® version 9.4 or later (SAS Institute,Inc., Cary, NC).

Statistical Methodology:

Summary statistics will be presented for continuous variables with descriptive statistics, including n, mean, standard deviation (SD), median, minimum, and maximum. For categorical variables including binary variables, frequency counts and percentages will be presented. P-values will be computed for each analysis group separately. In addition, 95% 2-sided confidence intervals (CIs) will be presented, where relevant. In case of percentages, the CI will be computed using the Clopper-Pearson method. The CI will be computed for continuous variables using t-test analysis. Summary statistics will be displayed by baseline groups.

Demographics and Baseline Characteristics:

Demographics will be presented in a summary table and in a by-subject listing, including age, gender, race, iris color, and ethnicity. Baseline characteristics, presented in a summary table and in a by-subject listing.

Prior Medical, Ocular and Treatment History:

All medical and ophthalmic histories reported at the screening and baseline visits will have their verbatim term mapped to their corresponding thesaurus terms using version 25.1 of the Medical Dictionary for Regulatory Activities (MedDRA) coding dictionary.

Efficacy Analysis:

Primary Efficacy Analysis

The primary efficacy endpoint parameters for the study are the mean CFB in total CFS and the mean CFB in modified SAnDE score at Week 12. Significance will be set at p<0.05 for the analysis of all groups and endpoints.

Secondary Efficacy Analysis:

Same as primary

Safety Analyses:

All safety analyses will be performed using the SAF population. No imputation of missing data will be performed. Safety analyses will be presented in summary tables and in by-subject listings.

Compliance:

Drug accountability data was assessed at each visit and used for further patient counselling but was not collected for analysis.

Adverse Events:

Adverse events will be coded according the MedDRA version that will be available at the time of the data cut-off. A treatment emergent AE (TEAE) is defined as an AE starting on or after the day of treatment. A serious AE (SAE) that is ongoing at the time of completion or discontinuation from the study will be followed until stabilization or resolution of the event.

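### The protocol's REML repeated-measures model and the SAP's t-test interval for the primary endpoints are not reconciled, and the SAP has no missing-data rule for efficacy

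*SAP*

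**What the plan says.** Protocol, synopsis, Statistical Analyses: "Primary efficacy endpoints will be analyzed using descriptive statistics and restricted maximum likelihood repeated measures mixed model (REMLMMRM) models". The next bullet promises multiplicity-adjusted significance levels for these endpoints. No fixed effects, covariance structure or visit contrast are given.

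SAP, introduction: "This analysis plan is based on the final protocol (Version 1.0) dated 11 FEB 2020". The primary endpoint is "the mean CFB in total CFS and the mean CFB in modified SAnDE score at Week 12 for all patients".

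SAP, Statistical Methodology: p-values are promised without naming a test, 95% two-sided intervals are to be shown where relevant, and "The CI will be computed for continuous variables using t-test analysis". Primary Efficacy Analysis repeats the two endpoints and sets the 0.05 threshold, with no model or test. The secondary efficacy analysis is to follow the primary.

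On who is analysed, the SAP says "All efficacy analyses will be performed using the ITT population". Besides one dose, ITT membership requires only that a subject "have at least 1 post-baseline assessment". Subjects who withdraw after consent and having "received the study treatment will not be replaced". On timing: "The efficacy analysis will be performed after all subjects have completed Week 12 or discontinued prior to Week 12". The only sentence on imputation, which rules it out, stands under Safety Analyses, directly after the sentence naming the safety population.

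**The concern.** The two documents lead an analyst to different primary results. A repeated-measures model uses every recorded visit of every ITT subject. A one-sample t-test on Week 12 change uses only subjects with a Week 12 value, although the SAP says the efficacy analyses use the whole ITT set. Neither method is fully specified, and the SAP does not say whether it keeps or replaces the protocol's model.

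The trial has one arm. No control group is exposed to the same dropout, so any selection among completers goes straight into the estimated improvement. Because the secondary analysis follows the primary, the continuous secondary endpoints inherit the gap.

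**Working it through.** **1. The two documents side by side**

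| Item | Protocol synopsis | SAP |
|---|---|---|
| Model for primary endpoints | REML repeated-measures mixed model, plus descriptive statistics | None stated |
| Test for primary p-values | Implied by the model | Not named; sidedness not stated |
| Interval, continuous data | Not stated | t-test based, 95% two-sided |
| Multiplicity, primary endpoints | Adjusted levels to be presented | 0.05 for each; no adjustment described |
| Missing efficacy data | Not stated | Not stated (no-imputation sentence is under safety) |

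There is no figure in the plan to reproduce: the supplied text gives no sample size, SD, effect size or dropout rate.

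**2. Why the methods can differ.** Let m be the share of ITT subjects without a Week 12 value. The ITT mean change is (1 - m) × (mean in observed) + m × (mean in missing). Hence

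observed-case error = m × (mean in observed - mean in missing).

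The error is zero if m = 0 or if dropouts and completers would have changed equally. Its sign follows who leaves.

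**3. Size under assumed inputs.** All inputs here are assumptions: N=100; unit-variance outcomes at baseline and Weeks 4, 8 and 12; between-visit correlation 0.4-0.8; true Week 12 change -0.5 SD; everyone has Week 4; later dropout depends on the last observed change, with poor responders leaving at a log-odds slope of 0.5-1.5 per SD; 4,000 replicates per setting. The REML fit used visit as fixed effect, baseline as a response, unstructured covariance and Kenward-Roger degrees of freedom.

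| Missing at Week 12 | Observed-case overstatement (SD) | Divided by 0.5 | t-interval coverage |
|---|---|---|---|
| 5% | 0.004-0.038 | 0.8-7.6%, about 1-8% | 93-95% |
| 10% | 0.009-0.075 | 1.8-15%, about 2-15% | 89-95% |
| 20% | 0.020-0.143 | 4-28.6%, about 4-29% | 78-94% |

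REML was within 1%, with coverage of 94.2-95.5% across the settings with dropout on observed values.

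A separate run at correlation 0.6, slope 1 and 10% missing gave observed cases -0.537 (coverage 93.8%) and a likelihood estimate of -0.499. The observed-case error is 0.037 SD, or 0.037/0.5 = 7.4%. By the identity in step 2, completers and dropouts differ by 0.037/0.10 = 0.37 SD.

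**4. Other mechanisms, same framework**

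- Dropout unrelated to response: no observed-case bias.
- Good responders leaving (slope -1): observed cases understate by 2-6% at 5% missing and 8-23% at 20%.
- Dropout on unobserved values: observed cases overstate by 1-11% at 5% and 6-42% at 20%; REML by 1-6% and 4-23%.

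**5. The significance verdict.** At -0.5 SD and N=100, with poor responders leaving, p<0.05 was reached in at least 99.4% of trials with observed cases and at least 98.2% with REML.

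**6. Does the model need Weeks 4 and 8?** Not entirely. In a two-timepoint check with dropout driven by baseline and a true change of -0.50, observed cases gave -0.41 and the likelihood estimate -0.50. Baseline alone contributes when it is modelled as a response.

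**The case against.** The other side has four arguments.

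- **The protocol's model still stands.** The SAP is based on the protocol and nothing withdraws the model; the t-test sentence sits in a general summary paragraph. This is a fair reading, but the SAP is the document that describes the final analysis, and it never adopts the model.
- **The t-test is plainly meant.** A two-sided 95% t-interval for a mean change excludes zero exactly when the two-sided one-sample t-test gives p<0.05, so the test can be inferred. That also is fair, but it would be an unexplained departure from the protocol. That both readings are reasonable is the defect.
- **The no-imputation sentence covers efficacy.** Its placement says otherwise. Even if extended, it would not choose between the two methods, since neither imputes.
- **The supplied protocol is only a synopsis.** This stands: a fuller version may hold model details, so the point is limited to the supplied documents.

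Some stronger readings are tempting but unsupported. A reader might infer that the estimator is wholly open, with last observation carried forward among the options. The documents name two candidates, and no section mentions carrying values forward. A reader might infer that early discontinuation is expected. The SAP only provides for it when timing the analysis and gives no rate. A reader might infer that the method was, or will be, picked after seeing results. Nothing in the documents shows that.

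**Conclusion.** The point holds as an unreconciled conflict between protocol and SAP on the primary analysis, together with an unstated missing-data rule for efficacy. It rests on the text and needs settling whatever the dropout turns out to be.

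The percentages only illustrate what could follow; they are not estimates for this trial. Under response-related dropout on observed values, the overstatement is small at 5% missing (about 1-8%) and can matter at 20% (about 4-29%). It vanishes if dropout is unrelated to response and reverses if good responders leave. Neither size nor direction in this trial can be found from the documents.

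A reader might infer that a t-test would make false-positive findings common. The simulations do not support that as a general statement. With no true change, a rate of 39% arose only in an extreme corner (N=200, 20% missing, slope 1.5, correlation 0.4); at N=100, 10% missing and slope 1 it was about 7%.

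**What to change.** In the SAP's Primary Efficacy Analysis, state the protocol's model as primary. Suggested content: for each primary endpoint, analyse baseline and all recorded post-baseline visits in the ITT population by a REML repeated-measures mixed model with visit as fixed effect; take the Week 12 change, its 95% interval and its two-sided p-value all from this model; impute nothing and assume data are missing at random. Unstructured covariance and Kenward-Roger degrees of freedom are reasonable specifications, but they are suggestions and not protocol text.

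Carry over the protocol's multiplicity adjustment for the two primary endpoints. Keep the Week 12 observed-case t-test as a sensitivity analysis and add a delta-adjusted one. If the t-test is meant to replace the protocol's model, the SAP should say so, give the reason and state the missing-data rule.

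The cost is SAP wording and a few lines of SAS, with no new data. The downsides are real but limited. The model relies on missing at random; if dropout depends on unobserved values, bias remains, at 40-61% of the observed-case bias in the scenarios run. The gain is larger if CFS and SAnDE were recorded at Weeks 4 and 8. The protocol schedules those visits, but the supplied text does not list these assessments by visit. Subjects with no post-baseline assessment stay outside ITT and are not recovered.

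### The protocol promises multiplicity-adjusted significance levels for the primary endpoints, but the SAP sets p<0.05 throughout, with no adjustment and no rule on whether one or both primaries must succeed

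*SAP*

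**What the plan says.** **Protocol, synopsis, Statistical Analyses.** On multiplicity: "Multiplicity adjustments of observed significance levels for primary efficacy endpoints will be presented". On the model: "Primary efficacy endpoints will be analyzed using descriptive statistics and restricted maximum likelihood repeated measures mixed model (REMLMMRM) models". No adjustment method is named.

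**SAP, opening text.** "This analysis plan is based on the final protocol (Version 1.0) dated 11 FEB 2020". The SAP does not say that the multiplicity commitment was withdrawn or changed.

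**SAP, Primary Efficacy Analysis.** "Significance will be set at p<0.05 for the analysis of all groups and endpoints". The secondary analysis is declared the same as the primary. The SAP text does not mention multiplicity, adjusted p-values, a split of alpha or an order of testing.

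**SAP, primary endpoint (under Study Objectives).** A singular heading introduces two measures: "the mean CFB in total CFS and the mean CFB in modified SAnDE score at Week 12 for all patients".

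**Objectives.** The SAP's primary objective is to "evaluate improvements in the signs and/or symptoms of DED following the use of CEQ". The protocol synopsis has the same and/or: "to evaluate improvement in the signs and/or symptoms of DED following use of CsA 0.09% ophthalmic solution".

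**SAP, Statistical Methodology.** P-values are produced separately for each analysis group, and the number of groups is not given. The only test named for continuous variables concerns intervals: "The CI will be computed for continuous variables using t-test analysis".

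**The concern.** A SAP should turn the protocol's statistical commitments into steps that an analyst can carry out. Here the commitment has no counterpart. Followed as written, the SAP compares each primary p-value with 0.05, unadjusted.

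Three choices are open in the text supplied: which adjustment to use, which p-values to adjust (mixed model or t-test), and whether one significant primary counts as success. All three could be settled after the results are known. In an open-label, single-arm study, fixing the analysis in advance is one of the few protections available. If either endpoint may carry the primary claim, two unadjusted tests also raise the chance of a false claim above the nominal level.

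**Working it through.** The documents give no family-wise error rate, power or sample size, so there is no figure of theirs to reproduce. The check has two parts.

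**1. What the wording implies about the success rule**

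| Text | Points to |
|---|---|
| Objective in both documents: signs and/or symptoms | Either endpoint suffices |
| Protocol: adjusted significance levels promised for the primaries | Either suffices (no adjustment is needed if both are required) |
| SAP: singular primary endpoint, two measures joined by *and* | Both required |

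None of these is stated as a decision rule.

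**2. Size of the error under each reading**

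*Inputs.* Two primary endpoints, each at 0.05 (SAP). The tests are taken as two-sided; the SAP says this only of its confidence intervals. The correlation ρ between the two test statistics is not given, so 0 to 0.9 is assumed. Critical values: 1.960 for two-sided 0.05 and 2.241 for two-sided 0.025.

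*Formulas*, with (Z1, Z2) standard bivariate normal, correlation ρ, and neither endpoint truly changing:

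- Either suffices, any direction: 1 − P(|Z1| < 1.960 and |Z2| < 1.960). At ρ = 0: 1 − 0.95² = 0.0975.
- Either suffices, false improvement only: 1 − P(Z1 < 1.960 and Z2 < 1.960). At ρ = 0: 1 − 0.975² = 0.0494.
- Holm, any direction (the first step decides whether there is any false claim): 1 − P(|Z1| < 2.241 and |Z2| < 2.241). At ρ = 0: 1 − 0.975² = 0.0494.

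| ρ | Either, any direction | ÷ 5% | Either, improvement only | ÷ 2.5% | Holm, any direction |
|---|---|---|---|---|---|
| 0 | 9.75% | 1.95 | 4.9% | 1.98 | 4.9% |
| 0.5 | 9.1% | 1.81 | 4.5% | 1.81 | 4.6% |
| 0.7 | 8.3% | 1.67 | 4.2% | 1.67 | 4.3% |
| 0.9 | 7.0% | 1.41 | 3.5% | 1.41 | 3.6% |

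- Both required: a false claim needs both tests significant, so the error cannot exceed 5%. It approaches 5% only when one endpoint truly changes and the other does not. With neither changing it is 0.05² = 0.25% at ρ = 0.

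**3. Power cost of Holm if either suffices**

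Assume each endpoint alone has 80% power at two-sided 0.05 (not given in the documents). The mean of each statistic is then 1.960 + 0.842 = 2.802. At 0.025, the power of one test is P(Z > 2.241 − 2.802) = 71.2%. At ρ = 0, the chance of at least one win is 1 − 0.20² = 96.0% unadjusted and 1 − 0.288² = 91.7% under Holm. Under Holm both endpoints win if both have p<0.05 and at least one has p<0.025.

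| ρ | At least one win: unadjusted → Holm | Loss (points) | Both win: unadjusted → Holm |
|---|---|---|---|
| 0 | 96.0% → 91.7% | 4.3 | 64.0% → 63.2% |
| 0.5 | 91.3% → 85.3% | 6.0 | 68.7% → 67.7% |
| 0.7 | 88.7% → 82.0% | 6.8 | 71.3% → 70.0% |
| 0.9 | 85.0% → 77.4% | 7.7 | 75.0% → 72.8% |

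**The case against.** **The two documents can be reconciled.** A reader might infer that the SAP overrides the protocol. The text does not establish that: 0.05 could be the threshold for adjusted p-values, and adjusted values can be presented beside raw ones. This stands as far as it goes. But the SAP does not say so, and no adjustment is named in either text, so the reconciled reading cannot be carried out.

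**Both endpoints may be required.** The SAP's singular endpoint joined by *and* supports this, and there would then be no inflation. A reader might take the and/or objective and the promised adjustment as proof that one endpoint is enough. They are not proof: the protocol says only that adjustments will be presented and gives no decision rule. The objection makes the inflation conditional; it does not supply the missing rule.

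**Only improvement matters.** A reader might infer from the 9.75% that the chance of wrongly claiming benefit is nearly 10%. That figure counts worsening too. For improvement, which is what the objective names, the rate stays below 5%. The ratio to nominal is essentially unchanged.

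**The full protocol may name a method.** The protocol text available is headed as a summary and synopsis, while the SAP rests on the final Version 1.0. That stands. The SAP, however, points to no such method.

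**The practical weight is limited.** This is an uncontrolled phase 4 study of change from baseline, with entry thresholds on the same two measures. Regression to the mean threatens the primary claim whatever adjustment is used. That stands too: the case for the change rests on the plan's own commitment, not on the error rates alone.

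**Conclusion.** The point holds in a limited form. The SAP does not carry out the protocol's commitment to adjusted significance levels, and neither text supplied states whether one or both primaries must succeed. Followed literally, the SAP tests both primaries unadjusted.

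The statistical consequence depends on the missing rule: an error of about 1.4 to 2 times nominal if either endpoint suffices, and none if both are required. These figures rest on two-sided tests and the assumed range of correlation.

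The documents do not support saying that the SAP irreconcilably contradicts the protocol, that either-endpoint success was intended, or that no method exists anywhere in the full protocol. Nor would adjustment make the single-arm comparison more convincing; it controls chance error only. This should be fixed, as a repair of the plan's wording.

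**What to change.** In the SAP, Primary Efficacy Analysis, replace the sentence that sets p<0.05 for everything. Adding text beside it would leave the conflict in place. Suggested wording:

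> The two primary endpoints, Week 12 CFB in total CFS and in modified SAnDE, are tested in all ITT patients with the Holm procedure at a two-sided family-wise 0.05, using the Week 12 p-values from the REML repeated-measures mixed model named in the protocol; raw and Holm-adjusted p-values are presented. P-values for baseline groups and secondary endpoints are nominal and descriptive.

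The Holm-adjusted values are twice the smaller p-value (at most 1) and, for the other endpoint, the larger of that value and its own p-value. Holm is one suitable choice; the protocol's commitment does not require it in particular. The model's covariates and covariance structure also need stating before the raw p-values are fully fixed in advance.

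If the sponsor instead requires both endpoints, the SAP should say so, keep each at 0.05, and reconcile this with the protocol's adjustment sentence and the and/or objectives.

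**Cost.** SAP wording only, with no new data. Under Holm at least one primary must reach p<0.025, which brings the power loss tabulated above: about 4 to 8 points for at least one win, and about 1 to 2 points for both. The both-required alternative changes no test level.
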